3.2.1 Inclusion Criteria

Patients fulfilling the following criteria are included in the study:

- Patient has purchased warfarin (Anatomical Therapeutic Chemical classification (ATC) code B01AA03) between 01-Jan-2007 and 31-Dec-2009,
- Patient has at least one INR measurement available between 01-Jan-2007 and 31-Dec-2009, and
- Patient has a International Classification of Diseases (ICD-10 version 10) diagnosis code I48 for AF between 01-Jan-2005 and 31-Dec-2009.

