3.3 Data Source/Data Collection Process

The study timelines are presented in the picture below:

Figure 3.3-1: Study Timelines

[figure not shown]

Table 3.3-1: Study Registers

Register	Register Holder	Information obtained
National Prescription Register	Kela – The Social Insurance Institution of Finland	Drug purchases (ATC codes)
National Reimbursement Register	Kela	Reimbursement decisions 207 for chronic arrhythmias (for population characterization)
Finnish Care Register, HILMO	National Institute for Health and Welfare	Diagnoses (ICD10 codes) and date of diagnosis
National Causes of Death Register	Statistics Finland	Time of death and causes of death (ICD-10 codes)
Laboratory databases	HUSLAB + other hospital laboratories	INR measurements and other relevant laboratory values
Finnish Cancer Registry	National Institute for Health and Welfare	Cancer diagnosis (ICD-O-3 codes) and date of diagnosis
Population Register	Population Register Center	Places of domicile 12 months prior to and on index dates.
Social HILMO	National Institute for Health and Welfare	Information (dates) about institutionalization (other than hospitalization)

- Data will be requested from the registry holders ([Table 3.3-1](#)) based on the study protocol.
- Data permits will be requested from each registry holder based on the study protocol and ethical approval.
- Approval of Ethical Review Board of Hospital District of Helsinki and Uusimaa (HUS) will be requested to cover the nationwide study.
- This is a fully register-based study and patients will not be contacted in any phase of the study.
- Warfarin exposure will be defined by Kela, who then will convert the patient IDs to study IDs (SIDs). Kela will then send the IDs and the SIDs to other register holders: Statistics Finland, National Institute for Health and Welfare, Statistics Finland, Population Register Center, and central hospital laboratories included in the study.
- EPID Research will receive unidentifiable data including SIDs only. All patient data handled by the researchers are then anonymous which ensures full data protection of the patients.

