3.4 Definitions of Study Variables

3.4.1 Outcomes/Endpoint Variables

The studied primary outcomes/endpoint variables of interest are defined through ICD-10 diagnosis codes (hospitalizations and deaths) or ICD-O-3 codes (cancers). See [Appendix 1](#) and [2](#) for more detail.

The time to event for each primary outcome will be calculated as the time from the index date to the time of the diagnosis of the outcome when such an event occurs during the follow-up.

Index date is defined as the date of first purchase of warfarin after 01-Jan-2007. Follow-up of the patients starts on the index date, and ends on 31-Dec-2011, at time of death or at time of emigration whichever occurs first. Treatment and comorbidity history is gathered from the period 01-Jan-2005 to 31-Dec-2006.

Primary outcomes:

- Stroke
- Other systemic thromboembolic events excluding stroke
- Myocardial infarction
- Bleeding events
- Mortality all-cause
- Mortality (stroke)
- Mortality (myocardial infarction)
- Mortality (systemic thromboembolic events excluding stroke)
- Mortality (bleeding events)

The studied secondary outcomes/endpoint variables of interest are anemia and renal impairment.

Time to anemia is defined as the time from index date to time of first decrement of 20 g/L in haemoglobin or time when haemoglobin is under the reference value.

Time to renal impairment is defined as the time from index date to time when creatinine is under the reference value.

Secondary outcomes

- Anemia
- Renal impairment

In the statistical analysis follow-up for each time to event outcome continues until the time of the event, death, emigration or 31-Dec-2011 whichever comes first.

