4.1.3 Exploratory Objectives

Objective 1: Stratified incidence rates with 95% CIs will be estimated for anemia as endpoint within the strata of the exposure variables (INR levels and TTR categories) and other covariates.

The crude and adjusted hazard ratio (HR) estimates with 95% CIs and P-values will be estimated separately within the INR levels and TTR categories using the conventional Cox's proportional hazards model adjusting for other covariates. For INR the category 2.0–3.0 will be used as the reference category. Similarly for TTR the category $\geq 60\%$ of time will be used as the reference category.

Objective 2: Discontinuity period of warfarin treatment due to a surgical operation or intervention is identified as starting two weeks before and ending two weeks after such procedure.

Stratified incidence rates with 95% CIs will be estimated for stroke, systemic thromboembolic events, myocardial infarction, and bleeding events in the strata of other covariates within periods of warfarin discontinuity. Also, an indicator variable of the discontinuity period will be added to the Cox's proportional hazards model.

Sensitivity analysis will be done to study the robustness of the discontinuity period definition.

Objective 3: The distribution of days taken to achieve INR target in the new warfarin user population will be provided. Stable INR-target is considered achieved after 3 consecutive INR measurements are within the target 2.0-3.0.

Objective 4: For the new warfarin user population the distribution of TTR at 1, 6, and 12 months after start of warfarin treatment stratified by other covariates. For the prevalent warfarin user population the distribution of TTR at the end of 2010 and 2011 stratified by other covariates.

Objective 5: Warfarin users will be tabulated by use of antiarrhythmic medication (yes/no) at start of follow-up and during follow-up. During follow-up users will also be stratified by the INR and the TTR levels.

Objective 6: Warfarin users will be tabulated by use of interaction medication (yes/no) at start of follow-up and during follow-up. During follow-up users will also be stratified by the INR and the TTR levels.

Objective 7: Warfarin users will be tabulated by comorbidities.

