5 STUDY LIMITATIONS/STRENGTHS

Finland has a well-developed population register system with tens of years of longitudinal follow-up data. The persons are identified in the registers with a unique personal identification number enabling linkage between different registers. These data has not been collected for study purposes, which may affect the quality of the data. However, these registers have been considered reliable for scientific research purposes.

Only those citizens that have been living in Finland for 12 months prior to index date will be included in the study.

No exact prescribed dosing information is available. Dosing is assumed based on the information of purchases and package sizes with defined daily doses (DDDs).

Coverage of the Prescription Register containing reimbursement information of all permanent residents of Finland is about 97%. Missing data includes relatively inexpensive packages which are not reimbursed. Fully reliable information on eg, acetylsalicylic acid use is then not available.

Medications used during hospitalizations are not available. However, based on the hospital care register the hospitalization periods can be taken into account to define gaps in the drug treatment periods.

No nationwide database about laboratory measurements is available. The laboratory data is then collected from separate local central laboratories. All laboratory values for particular patients may then not be available. Also changes in places of domicile may affect the follow-up of the patients. On the other hand, previous published surveys on the subject have not included INR follow-up to this extend.

To avoid selection bias, the cohort time (years 2007 to 2009) was chosen to avoid complication of patients switching from warfarin to newer anticoagulant medications eg, dabigatran.

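### The follow-up rule for anemia and renal impairment counts person-time in which no laboratory result could show the event

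*Protocol*

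**What the plan says.** Protocol section 3.4.1 defines both outcomes by laboratory values alone. For anemia: "Time to anemia is defined as the time from index date to time of first decrement of 20 g/L in haemoglobin", or the time haemoglobin falls below its reference value. For renal impairment: "Time to renal impairment is defined as the time from index date to time when creatinine is under the reference value". The same section closes with one rule for all outcomes: "In the statistical analysis follow-up for each time to event outcome continues until the time of the event, death, emigration or 31-Dec-2011", whichever is first.

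The laboratory values come from "HUSLAB + other hospital laboratories" (Table 3.3-1), not from a national source. The only laboratory condition for entry is "Patient has at least one INR measurement available between 01-Jan-2007 and 31-Dec-2009" (section 3.2.1); no haemoglobin or creatinine result is needed. Section 5 concedes that "All laboratory values for particular patients may then not be available" and adds "Also changes in places of domicile may affect the follow-up of the patients". Table 3.3-1 lists domicile only for the 12 months before index and at index.

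Section 2.3, Exploratory Objective 1, plans an INR comparison for both outcomes. Section 4.1.3 describes the analysis for one: "Stratified incidence rates with 95% CIs will be estimated for anemia as endpoint within the strata of the exposure variables", followed by Cox hazard ratios by INR level and TTR category.

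**The concern.** The follow-up rule suits events taken from the national care and cause-of-death registers, where a resident is observable every day until death or emigration. It does not suit an event that exists in the data only on a day when a participating laboratory reports a result. Someone with no haemoglobin result, or whose last one was early in follow-up, adds event-free years in which no event could have been recorded. A later move out of a laboratory area would not show in the domicile data listed. Section 4.1 carries the last INR forward over gaps longer than 60 days with no stated limit, so this time is still assigned to an INR stratum.

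Two things are at stake in Exploratory Objective 1: the absolute rates, and the INR contrasts for anemia. An abnormal value is charged to the INR category in force when blood is drawn. If blood counts are more frequent at some INR levels than at others, those levels collect more anemia without any difference in true onset.

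**Working it through.** **1. The plan's own denominator.** Section 4.2: 3,000,000 × 1.6% × 67% = 32,160, stated as 32 000; 32 000 × 3 years = 96 000 person-years, as stated. The protocol gives no rate, testing frequency or laboratory coverage for haemoglobin or creatinine. Everything below rests on assumed inputs and shows size only.

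**2. Unobservable time alone.** Let λ be the true onset rate, T the follow-up and c the share of patients whose tests are captured. Onset is exponential, captured patients are detected at once, and the others contribute T event-free years.

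Observed rate = c(1 − e^(−λT)) / [c(1 − e^(−λT))/λ + (1 − c)T]

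With λ = 0.06 and T = 3, 1 − e^(−0.18) = 0.16473.
- c = 0.9: 0.14826 / (2.4709 + 0.3) = 0.0535, ratio to truth 0.89
- c = 0.8: 0.13178 / (2.1964 + 0.6) = 0.0471, ratio 0.79
- c = 0.5: 0.08236 / (1.3727 + 1.5) = 0.0287, ratio 0.48

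For true rates of 3 to 20 per 100 person-years over 3 years, the ratio is 0.87–0.90 at 90% capture, 0.75–0.79 at 80% and 0.43–0.49 at 50%.

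**3. The opposing effect.** Section 3.4.1 does not require haemoglobin to be normal at index. Let a share p of captured patients be already low and found at 0.25 years, with c = 0.8, λ = 0.06, T = 3.
- p = 5%: events 0.8 × (0.05 + 0.95 × 0.16473) = 0.1652; person-years 0.8 × (0.05 × 0.25 + 0.95 × 2.7455) + 0.6 = 2.6966; rate 0.0613, ratio 1.02
- p = 10%: events 0.1986, person-years 2.5968, rate 0.0765, ratio 1.27

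So 5% prevalent low haemoglobin offsets a 20% capture loss, and 10% reverses it.

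**4. INR contrast when testing differs.** Assume identical onset at every INR level (6 per 100 person-years, 3 years) and detection at the next test, with k tests per year.

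If each patient stays in one category, the share detected is F = 1 − (k·e^(−λT) − λ·e^(−kT))/(k − λ), and mean person-time is S = [k(1 − e^(−λT))/λ − λ(1 − e^(−kT))/k]/(k − λ). For k = 2: F = 0.1390, S = 2.815, F/S = 0.0494, or 0.823 of the true rate. The same step gives 0.668, 0.881 and 0.910 for k = 1, 3 and 4. Apparent rate ratios: 3 against 2 tests, 0.881/0.823 = 1.07; 4 against 2, 0.910/0.823 = 1.11; 4 against 1, 0.910/0.668 = 1.36.

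If patients switch category, the effect grows with the speed of switching. The table gives simulated rate ratios against INR 2.0–3.0, with categories drawn at 21.7/63.6/14.7% (section 4.2) and noise of a few hundredths. Test rates are for INR under 2.0 / 2.0–3.0 / over 3.0.

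| Category redrawn about every | 3/2/3 tests per year (under 2.0; over 3.0) | 3/2/4 tests per year (under 2.0; over 3.0) |
|---|---|---|
| 365 days | 1.19; 1.17 | 1.12; 1.23 |
| 90 days | 1.28; 1.32 | 1.31; 1.54 |
| 28 days | 1.39; 1.40 | 1.41; 1.78 |

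Equal testing gives about 1.0.

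**The case against.** The strongest reply has five parts.

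- **Direction.** A reader might infer that the rates will be too low. The documents do not support this. Patients already below the reference value at index count as events, and step 3 shows that modest prevalence cancels or reverses the deficit. This stands.
- **INR contrasts.** A reader might infer that the hazard ratios measure testing frequency. That requires testing to differ by INR level, and the protocol gives no testing rates. The size also depends on how fast INR categories change. This stands: the distortion is a conditional risk.
- **The 20% figure.** Section 4.2 reduces the study population by 20% in case INR measurements are unavailable. It is tempting to read this as missing haemoglobin time, but it concerns INR and the power calculation. The 80% capture above is only an assumption.
- **Renal impairment.** Section 4.1.3 describes no renal rate or hazard ratio, and section 3.4.1 words the event as creatinine below its reference value. No direction of error can be read for that outcome.
- **Disclosure and stakes.** Section 5 discloses missing laboratory data, hospital district is a covariate, details are deferred to the SAP, and the objective is exploratory. This limits the weight of the point but does not answer it. Disclosure does not change the denominator, district cannot capture patient-level testing, and the follow-up rule is fixed in the protocol itself.

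**Conclusion.** The point holds in a limited form. Section 3.4.1 fixes a person-time rule under which laboratory-defined outcomes accrue time that cannot yield an event. Taken alone, this lowers the rate to about 0.79 of the truth at an assumed 80% capture, 6 per 100 person-years and 3 years. The net direction is unknown, because prevalent low haemoglobin acts the other way. If testing differs by INR level, apparent rate ratios for anemia of about 1.1 to 1.8 could arise with no true difference, under the assumed 3/2/3 and 3/2/4 test rates and depending on switching speed.

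Only Exploratory Objective 1 is affected; the primary outcomes are not laboratory-defined. For renal impairment, the definition in section 3.4.1 must be reconciled with the Appendix 2 reference limits, and the aim in section 2.3 with the missing analysis in section 4.1.3. The rule should be changed, but it does not threaten the study's main results.

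**What to change.** Give laboratory-defined outcomes their own at-risk rule in section 3.4.1.

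- **Start:** a haemoglobin (creatinine) result on or shortly before index, or failing that the first result after it, that does not already meet the definition. This removes prevalent cases and gives the 20 g/L decrement a starting value.
- **Person-time:** count it only within a fixed window after the most recent captured test, for example 6 months, and vary the window in sensitivity analyses. Patients with no result contribute none. A forward window is preferable to stopping at the last result, which conditions on future testing. State how an abnormal result arriving after the window has closed is handled.
- **Testing frequency:** report haemoglobin and creatinine tests per person-year by INR category. Adjust for it at most as a sensitivity analysis, since testing may itself follow from bleeding or anemia.
- **Renal impairment:** reconcile the definition, and either describe its analysis in section 4.1.3 or drop it from the objective.

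The window does not remove differences in testing within it, which is why the frequencies must be reported. The laboratory data are already requested. The cost is protocol and SAP wording, programming, and fewer person-years for these two outcomes.

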3.4.2 Exposure/Independent Variables of Interest

- Performance of warfarin therapy
 - INR values under 2.0, 2.0-3.0, and over 3.0
 - time to reach the target INR 2.0–3.0
 - TTR, percentage of time during which the interpolated INR values lie between 2.0 and 3.0¹³
- Exposure to warfarin (ATC B01AA03)
 - new vs. prevalent users (< vs. > 90 days)
 - time since discontinuation
- I48 diagnosis
 - yes/no
 - time from the diagnosis
- Place of domicile 12 months prior to and on the index date
 - if not in Finland, excluded
- Use of antiarrhythmic drugs:
 - yes/no
 - ◆ Group C01B: antiarrhythmic drugs, classes I and III (see [Appendix 3, Table 1](#) for details)
 - ◆ Group C07: beta blockers / class II antiarrhythmics (see [Appendix 3, Table 2](#) for details)
 - ◆ C08DB01: diltiazem (class IV antiarrhythmic)
 - ◆ C08DA01: verapamil (class IV antiarrhythmic)
- Use of other anticoagulant or reimbursed antithrombotic therapy:
 - heparins (B01AB01, B01AB51), clopidogrel (B01AC04), dipyridamole (B01AC07), ticlopidine (B01AC05), prasugrel (B01AC22)

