2 OBJECTIVES

2.1 Primary Objectives

- 1) To investigate and compare risk of stroke, systemic thromboembolic events, and myocardial infarction among AF patients in relation to INR levels: under 2.0, 2.0-3.0, and over 3.0.
- 2) To investigate and compare risk of bleeding events among AF patients in relation to INR levels: under 2.0, 2.0-3.0, and over 3.0.
- 3) To investigate and compare mortality risk among AF patients in relation to INR levels: under 2.0, 2.0-3.0, and over 3.0.

The primary objectives are evaluated separately for prevalent users of warfarin and for new users of warfarin.

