3 STUDY DESIGN

3.1 Overview of Study Design

The study with cohort design is conducted as a nationwide retrospective register-based linkage study using data obtained from the Finnish health care registers. The study population consists of all AF patients using warfarin with INR measurements in selected hospital district areas in Finland between 01-Jan-2007 and 3-Dec-2009.

Index date: Index date is defined as the date of first purchase of warfarin after 01-Jan-2007.

Follow-up period: Follow-up of the patients starts on the index date, and ends on 31-Dec-2011, at time of death or at time of emigration whichever occurs first.

History period: Treatment and comorbidity history is gathered from the period 01-Jan-2005 through 31-Dec-2006.

The key milestones of the study process are given below (Table 3.1-1). Note that the timelines are estimates only and are subject to change depending on the duration of the data permission processes and actual receipt of the data from the register holders.

Table 3.1-1: Study Timelines

Milestone	Anticipated date
Study protocol approved	4-Mar-2013
Registration in the ENCePP e-Register	30-Apr-2013
Ethics committee approval	30-Apr-2013
Data permit approvals	30-Jun-2013
Receipt of data from register holders	30-Sep-2013
Final study report	30-Dec-2013

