4 STATISTICAL ANALYSIS

4.1 Statistical Analysis Methods

Data management, tabulations, graphics, and statistical modeling in carried out with R language (<http://www.r-project.org>). R language is described more detailed in report "R: Regulatory

Compliance and Validation Issues: A Guidance Document for the Use of R in Regulated Clinical Trial Environments" (<http://www.r-project.org/doc/R-FDA.pdf>)

A separate statistical analysis plan (SAP) including detailed statistical analysis and outputs will be produced by EPID research prior to performing any analysis.

Study population: The study population will be described at baseline (start of follow-up) using by previous drug exposure and other covariates.

Study outcomes: All study outcomes will be summarized by drug exposure and other covariates.

Drug exposure: Drug exposure starts at date of purchase. The length of the exposure period is calculated as $DDD/dose \times 1.5$, where DDD (daily defined dose) is the total amount purchased and “dose” is the amount used daily (one for an average person). For the first purchase “dose=1” and for other purchases the “dose” is calculated from previous use by dividing the previous DDD with the time between the present and the previous purchase.

The impact of the multiplier 1.5 in the construction of drug exposure will be evaluated for the primary objectives in sensitivity analyses by using multiplier values 1.25, 1.5 and 2. We will also perform a sensitivity analysis for the primary objectives by including only those patients with at least two purchases of prescriptions within a clinically meaningful timeframe of 3 months after the index date.

INR levels: Daily INR levels are calculated:

- 1) As the previous recorded INR measurement
- 2) By linear interpolation between two consecutive INR measurements. If the gap between the measurements is more than 60 days the previous measurement is applied.

Daily INR estimates are categorized into levels: under 2.0, 2.0-3.0, over 3.0. In addition when appropriate a finer categorization is used: under 1.5, 1.5-2.0, 2.0-3.0, 3.0-4.0, 4.0-5.0, 5.0-9.0, and over 9.0. This finer categorization will be used only in the analysis of the primary objectives.

Time in therapeutic range (TTR): The INR target value for AF patients is 2.0-3.0. In addition for stroke, systemic thromboembolic events, and myocardial infarction INR target above 2.0 is considered and for bleeding events INR target under 3.0 is considered.

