4.1.1 Primary Objective

Objectives 1-3: Stratified incidence rates with 95% confidence intervals (CIs) will be estimated for each primary endpoint within the strata of the exposure variables (INR levels and TTR categories) and other covariates, including history of AF prior the index date.

The crude and adjusted hazard ratio (HR) estimates with 95% CIs and P-values will be estimated separately within the INR levels and TTR categories using the conventional Cox's proportional hazards model adjusting for other covariates. For INR the category 2.0–3.0 will be used as the reference category. Similarly for TTR the category $\geq 60\%$ of time will be used as the reference category.

The objectives will be evaluated separately for the prevalent warfarin user population and the new warfarin user population. The new warfarin user population consists of those patients who initiate warfarin treatment during the follow-up (01-Jan-2007 to 31-Dec-2009).

A further sensitivity analysis will be performed where the adjusted HRs are estimated stratifying by the history of AF prior to the index date.

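### New and prevalent warfarin users, the two populations for every primary analysis, are defined in two unreconciled ways, so assignment is undetermined and can be wrong

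*Protocol*

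**What the plan says.** Section 2.1 makes the split govern all three primary objectives: "The primary objectives are evaluated separately for prevalent users of warfarin and for new users of warfarin". Two sections then say who belongs where.

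- Section 3.4.2, under exposure to warfarin: "new vs. prevalent users (< vs. > 90 days". No starting point is given, and exactly 90 days falls in neither group.
- Section 4.1.1: "The new warfarin user population consists of those patients who initiate warfarin treatment during the follow-up (01-Jan-2007 to 31-Dec-2009". This classifies patients. It mentions neither 90 days nor a drug-free period.

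The index date does not settle the matter, because it is the same for everyone: "Index date is defined as the date of first purchase of warfarin after 01-Jan-2007" (Section 3.1). A long-term user's first refill in 2007 and a true first prescription both qualify.

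Three other parts of the protocol bear on the question:

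- Section 4.1 models exposure per purchase. "The length of the exposure period is calculated as" total DDD bought, divided by daily dose, times 1.5. The dose "is the amount used daily (one for an average person" is set to 1 for the first purchase and derived from the preceding refill interval afterwards. Sensitivity analyses are run "by using multiplier values 1.25, 1.5 and 2".
- Section 4.1.2 (Objective 3) takes treatment as stopped only when more than 2 months have passed since the last exposure and INR measurement, with 1 and 3 months as sensitivity values.
- Section 4.1.3 (Objective 4) reports TTR in the new-user population at 1, 6 and 12 months.

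**The concern.** Every primary hazard ratio and incidence rate is to be reported within these two populations, and the protocol gives two rules for forming them. A statistical analysis plan could choose one, but it would then depart from the other, so this is a conflict between stated rules and not merely deferred detail.

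Secondary objective 1 (events in the first 90 days after initiation) and exploratory objectives 3 and 4 (time to INR target, TTR after start) also depend on identifying true initiation. A long-term user wrongly counted as an initiator has already passed the early risk period and is likely to be on a settled dose. Such patients would tend to lower the apparent early event rate, shorten the time to target and raise early TTR.

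**Working it through.** The protocol states no figure that depends on this definition, so there is none to reproduce. The check takes each reading of the 90 days in turn.

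**Reading 1: time on warfarin.** This fits the other use of 90 days in the protocol, as time since initiation in secondary objective 1. An initiator is new until about day 90 and prevalent afterwards. Section 4.1.1 instead keeps the patient in the new-user population, and Section 4.1.3 still analyses new users at 6 and 12 months, when Reading 1 would leave none. As an illustration, the 3-year mean follow-up planned for the whole cohort (Section 4.2) gives 90 / (3 × 365) = 90/1095 = 8% of an initiator's person-time as new, against 100% under Section 4.1.1.

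**Reading 2: no purchase in the 90 days before index.** This can serve as a working rule for initiation, so it does not clash with Section 4.1.1 directly. It has to be compared with the exposure and stopping rules.

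*Still exposed on day 90.* Exposure days = DDD / dose × multiplier. With dose = 1, exposure passes day 90 when DDD > 90 / multiplier:

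- multiplier 1.25: 90/1.25 = 72 DDD
- multiplier 1.5: 90/1.5 = 60 DDD
- multiplier 2: 90/2 = 45 DDD

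*Not yet stopped on day 90.* Assume that 2 months is 60 days, counted from the end of modelled exposure. Treatment has not ended by day 90 when DDD > (90 − 60) / multiplier:

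- multiplier 1.25: 30/1.25 = 24 DDD
- multiplier 1.5: 30/1.5 = 20 DDD
- multiplier 2: 30/2 = 15 DDD

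With the 3-month sensitivity gap taken as 90 days, (90 − 90)/1.5 = 0, so any purchase suffices. A later INR measurement postpones the stop further.

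*Examples at dose 1, multiplier 1.5 (purchase sizes are assumed).* A 100 DDD purchase is refilled on day 100. Exposure runs to day 150, and treatment could not be declared ended before about day 150 + 60 = 210. The patient is nevertheless a new user by a 90-day look-back. A 50 DDD purchase gives 75 days of exposure, so there is no overlap with day 90, but the stopping rule is not met until about day 75 + 60 = 135.

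*Steady refillers.* After the first purchase, dose = previous DDD / previous interval. For equal purchases every L days, exposure = DDD / (DDD/L) × 1.5 = 1.5 × L, and the purchase size cancels. If the formula is run over the 2005-2006 purchases, a patient who refills steadily every L > 90 days is modelled as exposed without a break, yet is a new user by a 90-day purchase look-back.

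**The case against.** Several counter-arguments carry weight.

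- The two defects belong to alternative readings. If 90 days is time on drug, the exposure length of a purchase is irrelevant. If it is a look-back, Sections 3.4.2 and 4.1.1 can be squared. This stands, and the two should not be added together. Each reading still collides with some other part of the protocol.
- A reader might infer that the 90-day cut is simply shorter than the exposure from one purchase. The protocol does not support that as a fact: it gives no DDD per purchase, and at dose 1 and multiplier 1.5 it is true only above 60 DDD.
- The DDD thresholds do not identify misclassified patients. Under a look-back, only users with a purchase gap over 90 days move. Someone buying 61-90 DDD and refilling on time at one DDD per day stays prevalent. This stands, and the share with long gaps is not given.
- Other readings exist. Ninety days free of modelled exposure would remove the steady-refiller problem. The Section 3.4.2 item might also be a separate covariate with a similar name. Either is possible, but the text states neither, and a protocol whose primary populations depend on guessing needs correcting.
- A missing washout length is commonly left to the analysis plan. That is fair for the length alone, but not for two stated rules that give different groups.

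**Conclusion.** The concern holds in limited form. The protocol gives two unreconciled definitions of the populations for all primary objectives. Under time on drug, the contradiction with Sections 4.1.1 and 4.1.3 is direct. Under a purchase-free look-back, continuing users can be labelled initiators while the protocol's own rules say their treatment never ended. The thresholds at dose 1 are 60 DDD for exposure (72 and 45 at the other multipliers) and about 20 DDD for the stopping gap. The latter assumes 60 days counted from the end of exposure.

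Two stronger conclusions that a reader might draw are not supported. The first is that patients are in fact misassigned throughout the primary analyses: assignment is undetermined, and the number affected is unknown. The second is a definite size of bias. For example, assumed 90-day rates of 6 and 3 per 100 person-years with 20% or 40% contamination give 0.8 × 6 + 0.2 × 3 = 5.4 and 0.6 × 6 + 0.4 × 3 = 4.8, which is 10% or 20% below 6. All of those inputs are assumptions, and none of them is an estimate from the protocol for initiators and long-term users.

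**What to change.** Use one patient-level definition, fixed at the index date, in both Sections 3.4.2 and 4.1.1. A new user has no warfarin purchase from 01-Jan-2005 to the day before index. A prevalent user has any such purchase. Remove the 90-day split from Section 3.4.2, and keep 90 days only as the time-since-initiation window for secondary objective 1.

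Section 3.1 already gathers treatment history for 2005-2006, so the change is one of wording, provided that this history includes warfarin purchases.

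There are two costs. The new-user group shrinks, because patients restarting after a break move to prevalent. In addition, 24 months of observable history cannot be assumed for everyone: Section 3.2.2 requires only 12 months of residence, so patients resident for 12-24 months before index have a shorter look-back. They should be flagged, or their influence checked in a sensitivity analysis.
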